4.12.5. Pharmacokinetics Analyses

Ataluren plasma concentrations will be listed. For ataluren plasma concentrations, those that are below the limit of quantification will be identified by "BQ" in listings. Those values that are missing will be left blank in listings.

4.12.6. New *Pseudomonas aeruginosa* Lung Infection

Any new *Pseudomonas aeruginosa* lung infection on treatment will be reported by the investigator. The proportion of subjects experiencing such event at least once will be summarized.

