Pulmonary involvement occurs in ~90% of patients, is usually among the most serious manifestations of the disease, and most commonly determines outcome [Ramsey 1996]. As early as 4 weeks of age, patients with CF begin to develop mucus plugging, bronchiectasis, neutrophilic invasion, and inflammation of airways [Khan 1995, Rosenfeld 2001]. High levels of the neutrophil chemoattractant interleukin-8 (IL-8) in the airways and sputum contribute to persistent neutrophilic inflammation and airway obstruction [Sagel 2007]. Over time, most patients develop chronic bacterial colonization/infection of the airways (characteristically with Pseudomonas aeruginosa, but also with Burkholderia cepacia, Haemophilus influenzae, Staphylococcus aureus, Escherichia coli, Klebsiella pneumoniae, and atypical mycobacterial species) resulting in infections and pulmonary dysfunction. Typically, CF pulmonary involvement manifests as an obstructive defect with air trapping and hyperinflation [Ramsey 1996, Tiddens 2002]. As the disease progresses, FEV₁ is reduced; it is estimated that FEV₁ declines by 1.9% per year in children and adolescents [FDA 1997]. Ultimately, chronic mucopurulent bronchiectasis leads to structural abnormalities and fibrosis, and the total lung capacity and forced vital capacity (FVC) decline. Progressive lung dysfunction leads to respiratory failure and death. The median age of survival is projected to be ~35 years of age if all genotypes are considered [Cystic Fibrosis Foundation 2003, Bellis 2006], but survival is generally shorter in patients with severe phenotypes [McKone 2006].

The primary goals of CF treatment are supportive, and include slowing the decline in lung function by clearing airways of mucus and by controlling respiratory infections, and maintaining nutritional status by providing pancreatic enzyme replacement therapy [Welsh 2001]. The first medical therapy approved by regulatory authorities for treatment/prophylaxis of the lung manifestations was dornase alfa (Pulmozyme®), a mucolytic enzyme that hydrolyzes neutrophil deoxyribonucleic acid (DNA) [Fuchs 1994]. Since that time, regulatory approval has been achieved for inhaled tobramycin (TOBI®) [Ramsey 1993, Ramsey 1999] and inhaled aztreonam

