14.4.6. New Pseudomonas Aeruginosa Lung Infection

In addition to the treatment of persistent *Pseudomonas aeruginosa* lung infection with inhaled antibiotics recommend by both European and CF treatment guidelines [Mogaygel 2013, Heijerman 2009] a growing body of evidence suggests that treatment of early Pseudomonas aeruginosa infection may be warranted, leading to a recommendation for early eradication therapy by the European Cystic Fibrosis Society [Heijerman 2009]. To investigate the extent to which ataluren may influence the occurrence of new Pseudomonas aeruginosa lung infection, the incidence of the occurrence of new positive cultures will be calculated. These airway cultures will be collected using the procedures and at a frequency (eg, quarterly) consistent with local standard of care. To limit reporting bias, the presence of *Pseudomonas aeruginosa*-positive cultures will be specifically elicited from the investigator.

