15.2 Benefits and Risks: Clinical Efficacy

Multiple Phase 2 and Phase 3 trials have now shown the potential benefit and safety of ataluren in the treatment nmCF in adults and children. Ataluren activity was demonstrated with TEPD testing in 2 separate Phase 2 trials (further details are provided in the ataluren Investigator Brochure).

Clinical benefit was further explored in the multicenter Phase 3 double-blind study (Study 009). In this 48-week study positive trends favoring ataluren were seen in the primary endpoint, the relative change from baseline in %-predicted FEV₁ at 48 weeks, which demonstrated a 3% difference between ataluren and placebo (-2.5% change on ataluren vs -5.5% change on placebo; p=0.124). An analysis of the relative change from baseline in %-predicted FEV₁ across all post-baseline study visits demonstrated an average difference between ataluren and placebo of 2.5% (-1.8% average change on ataluren vs -4.3% average change on placebo; p= 0.0478). A larger effect was seen in the patients not receiving chronic inhaled antibiotics. The effect of inhaled antibiotics was largely attributable to the use of inhaled aminoglycosides (ie, tobramycin). In patients not receiving chronic inhaled tobramycin at baseline, the Week 48 difference between the ataluren and placebo arms in the relative change of %-predicted was 5.7% (-0.7% change on ataluren vs -6.4% change on placebo difference in FEV₁).

The secondary endpoint, the rate of pulmonary exacerbations (ie, the number of pulmonary exacerbations in 48 weeks) also showed a positive trend in favor of ataluren, with the rate in the ataluren group being 23% lower than the placebo group (p=0.0992). In the patients not receiving chronic inhaled tobramycin, the pulmonary exacerbation rate in the ataluren group was 40% lower than the rate in the placebo group. These results show a consistent treatment effect of ataluren on both pulmonary function and exacerbation rates.

Collectively, the FEV_1 and pulmonary exacerbation data demonstrate the beneficial effect of ataluren in patients with nmCF aged 6 years and older. The increased effect seen in patients not receiving chronic inhaled tobramycin makes benefit more likely in these patients, who constitute the study population of this trial.

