3. STUDY POPULATIONS

3.1. As-Treated Population

The as-treated population consists of all subjects who took at least one dose of ataluren. This population will be used to analyze safety and treatment administration.

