4.12. Tertiary Analyses

All tertiary analyses will be performed for the As-Treated population, unless specified otherwise.

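### New *P. aeruginosa* infection is summarised over all As-Treated patients, with no rule for 'new' and no use of baseline culture status; an at-risk denominator would be a cheap improvement to one tertiary figure

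*SAP*

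**What the plan says.** **SAP 4.12.6** has two parts. On ascertainment, any new *P. aeruginosa* "lung infection on treatment will be reported by the investigator". On the summary, "The proportion of subjects experiencing such event at least once will be summarized". It names no population, look-back period or prior-negative requirement.

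**SAP 4.12** supplies the population: "All tertiary analyses will be performed for the As-Treated population, unless specified otherwise". **SAP 3.1** defines it: "The as-treated population consists of all subjects who took at least one dose of ataluren".

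**Protocol 14.4.6** describes the purpose as exploring how far ataluren may influence new infection, and says "the incidence of the occurrence of new positive cultures will be calculated". On the cultures themselves: "These airway cultures will be collected using the procedures and at a frequency (eg, quarterly) consistent with local standard of care".

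**Baseline status.** The schedule of events (Protocol Table 3, SAP Table 1) marks *P. aeruginosa* in sputum at Screening/Baseline. Footnote a lets the site skip it if Day 1 falls within 14 days of the Study 021 Week 48 visit. SAP 5.1 uses the Study 021 Week 48 assessment when the extension baseline is missing. Protocol 8.2.19, however, lists culture collection only from Week 12.

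**Status of the endpoint.** Protocol 3.3 lists it among the secondary endpoints and SAP 2.3.3 makes it tertiary. SAP 4.2 calls all analyses descriptive. SAP 6 does not list it among the analyses dropped after early termination, so it is still planned.

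**The concern.** A proportion of patients with a new infection is easiest to read when everyone in the denominator could have had one. Nothing here ensures that. The eligibility criteria (Protocol 4.2 and 4.3) do not mention *P. aeruginosa* status, and no other section restricts this analysis to patients free of it at baseline.

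Two things follow. First, the reported figure depends on how many patients were already positive on entry as well as on how often infection is acquired. Second, with no rule for 'new', one investigator may report only first acquisitions while another also reports reacquisition after eradication, so the numerator may mix two kinds of event.

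What is at stake is the meaning of one descriptive percentage, and whether it can be set beside figures from populations with a different baseline-positive share.

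**Working it through.** The plan gives no rate, precision or target for this endpoint, so there is no figure to reproduce. The check is what the stated denominator does to the result.

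**Inputs**

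- Denominator: all As-Treated patients (SAP 3.1, 4.12). About 200 are expected (Protocol 5.1). The factor below does not depend on this number.
- p: share already positive at extension baseline. Not in the documents; assumed 10 to 70%.
- k: frequency of events reported as 'new' in baseline-positive patients, relative to baseline-negative patients. Not in the documents; assumed 0 to 1.

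**Formula.** Let r be the proportion with an event among baseline-negative patients. The As-Treated proportion is (1−p)r + p·k·r. The understatement factor is r divided by this:

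1 / [(1−p) + pk]

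| p | k = 0 | k = 0.25 | k = 0.5 | k = 1 |
|---|---|---|---|---|
| 10% | 1.11 | 1.08 | 1.05 | 1.00 |
| 30% | 1.43 | 1.29 | 1.18 | 1.00 |
| 50% | 2.00 | 1.60 | 1.33 | 1.00 |
| 70% | 3.33 | 2.11 | 1.54 | 1.00 |

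For example, p = 50% and k = 0.5 give 1/(0.50 + 0.25) = 1.33. The direction is understatement whenever k is below 1; above 1 it would reverse.

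**Illustration, with assumed counts.** Take 200 treated, 100 of them negative at baseline, and 20 first infections among those 100.

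- k = 0: 20/200 = 10.0% (Clopper-Pearson 95% CI 6.2 to 15.0) of all treated, against 20/100 = 20.0% (12.7 to 29.2) of those at risk.
- k = 0.5: 10 further events in baseline-positive patients give 30/200 = 15.0%, against 20.0%.
- k = 1: 20 further events give 40/200 = 20.0%. The percentage now agrees with the at-risk one, but half the events behind it are in patients who were already positive.

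**Follow-up (secondary).** The proportion also takes no account of time at risk.

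- Inputs: Protocol 1 gives a first dose in Study 021 on 15 August 2014, an estimated 14-month recruitment and 48 weeks of treatment. SAP 2.1 gives 2 March 2017.
- Earliest entry: 15 August 2014 + 48 weeks = 17 July 2015, which is 84.9 weeks before that date.
- Latest entry: 15 October 2015 + 48 weeks = 15 September 2016, which is 24.0 weeks before it.
- At an assumed constant 0.20 first infections per at-risk patient-year, risk = 1 − exp(−0.20 × weeks/52.18): 8.8% at 24 weeks and 27.8% at 85 weeks.

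This range assumes that recruitment ran to the estimate, that there was no gap between studies, and that 2 March 2017 is the end of treatment. The SAP sentence can also be read as dating the decision. Patients who withdrew earlier have less follow-up.

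**The case against.** The strongest reply is that the understatement presupposes an estimand the SAP does not state. SAP 4.12.6 counts any new infection, experienced at least once. A patient whose earlier infection was eradicated can have such an event and may belong in the denominator. If such patients have events as often as the others, k = 1 and nothing is understated. This stands: the bias is conditional. It does not remove the need for a rule, because without one a reader cannot tell which k applies.

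A reader might infer that most patients are *P. aeruginosa*-positive at baseline, so that the figure is wrong by a factor of two or three. The documents do not support that. Protocol 2.1 says "Over time, most patients develop chronic bacterial colonization/infection of the airways (characteristically with Pseudomonas aeruginosa", but the sentence goes on to name other organisms and concerns bacterial colonisation in general, over time. Protocol 15.2 points towards a lower share, referring to "patients not receiving chronic inhaled tobramycin makes benefit more likely in these patients, who constitute the study population of this trial". The 3.3-fold entry needs both p = 70% and k = 0.

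A reader might also infer that the SAP contradicts the protocol, because Protocol 14.4.6 speaks of incidence. It does not. These documents use that word for plain percentages elsewhere (new-onset nephrolithiasis in Protocol 6.3.2; medications in SAP 4.8), and SAP 1 gives the SAP precedence.

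Other points against are partly met. Investigator reporting is a deliberate choice to limit reporting bias (Protocol 14.4.6), but it does not define 'new'. SAP 4.1 requires N, n, percentage, 95% CI and by-subject listings, so the denominator will be visible and an at-risk subset might be rebuilt where culture status was captured. That is weaker than planning it. Treatment duration and subjects per visit are tabulated (SAP 4.9, 4.5.1), but not for patients at risk of this event.

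**Conclusion.** The point holds in a limited form. By default SAP 4.12.6 uses all As-Treated patients, with no rule for 'new' and no use of baseline culture status. If already-positive patients have fewer 'new' events than the others, the figure understates the proportion among at-risk patients by 1/[(1−p)+pk]. Over the assumed grid this runs from 1.05 (p = 10%, k = 0.5) to 3.3 (p = 70%, k = 0), and it is 1.0 at k = 1. Since p, k and the infection rate are all assumed, the size cannot be fixed from the documents.

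Unequal follow-up after early termination is a secondary reason for caution, and its range rests on an estimated recruitment period and an ambiguous date. The endpoint is tertiary, descriptive and single-arm. No test or primary safety conclusion depends on it, so this is a minor improvement worth making.

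**What to change.** In SAP 4.12.6:

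- Define 'new' as a first positive on-treatment culture in a patient who is *P. aeruginosa*-negative at extension baseline (Visit 1, or Study 021 Week 48 under SAP 5.1) and has no positive result among the earlier cultures available. The second condition matters: with only one negative baseline culture required, a chronically infected patient could be counted as a new infection.
- Use those patients as the denominator, with the 95% CI that SAP 4.1 already requires.
- Report separately the counts with unknown baseline status, with no post-baseline culture, and with reacquisition.
- Keep the As-Treated proportion as a supplementary line.
- Optionally add, as a supportive figure, first new infections per 100 at-risk patient-years, with time running to first infection or last on-treatment culture.

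Protocol 8.2.19 and the schedule table should also be reconciled on whether a baseline culture result is collected.

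**Cost.** Some SAP wording, the table for this endpoint and a few counts; SAP 1 allows refinement by amendment before database lock. If the rate is added, at-risk time needs its own derivation, because the patient-years in SAP 4.10.1 are days on drug summed over all patients. The at-risk denominator is smaller and its CI wider. Some baseline status will probably be missing, and infection dates will be imprecise because culture frequency follows local practice.

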4.13. Interim Analyses

Interim safety analyses are planned when ~ 100 subjects have completed ≥ 36 weeks of treatment and when ~ 100 subjects have completed ≥ 72 weeks of treatment. Additional interim safety analyses may be performed based on the discretion of the DMC and will be described in the DMC charter. Based on the results of its deliberations, the DMC can recommend continuation of the study unchanged, study interruption, study termination, modification of the study, or alteration in the DMC monitoring plan.

The planned interim analysis will be based on the DMC Charter focusing on the safety review.

DATA HANDLING

5.1. Baseline

In general, Baseline is defined as the last non-missing valid assessment prior to or on the date of the first dose. The assessment at week 48 in study 021 will be used as the baseline if corresponding baseline in study 021e is missing.

5.2. Analysis Visits

Analysis visits are the scheduled visits in the protocol, unless specified otherwise. They are not derived via visit window mapping. Baseline is derived as noted in Section 5.1. Final Visit is derived as the last non-missing on-treatment visit during the study for each subject and included into the by-visit summary analyses. Early termination visit should also be derived as the visit right after the non-missing scheduled visit. For example, if the subject discontinued after Week 12, the early termination visit should be derived as Week 24.

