8.2.4. End of Treatment

The patient will return to the clinical research facility at Week 96 (Visit 9) for the End-of-Treatment visit. If the patient discontinues prematurely (ie, before Week 96), the procedures that would normally be performed at Week 96 should be performed as a Premature-Discontinuation Visit before the patient leaves the study.

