8.2.13. Renal Ultrasound

An ultrasound to examine the kidneys and collecting system will be performed at Screening/Baseline (Visit 1), Week 48 (Visit 5) and Week 96 (Visit 9 – End of Treatment/Premature Discontinuation) visit. The ultrasound examination will be performed according to local standards and a final interpretation and report will be provided by a local qualified expert. The findings will be captured in source documents and within the CRF.

A follow-up renal ultrasound may also be performed at any time during the study as clinically indicated at the discretion of the investigator. The PTC medical monitor must be informed via e-mail that an additional renal ultrasound was obtained and the serious adverse event reporting process should be followed, if applicable.

8.2.14. 12-Lead ECG

A 12-lead ECG will be obtained at Screening/Baseline (Visit 1), Week 48 (Visit 5), Week 96 (Visit 9 – End of Treatment/Premature Discontinuation) visit, and at the Post-Treatment Visit (4 weeks post discontinuation of study drug). The ECG will be performed and interpreted locally for clinical significance. The findings will be captured in source documents and with the CRF.

A follow-up ECG may also be performed at any time during the study as clinically indicated at the discretion of the investigator. The PTC medical monitor must be informed via e-mail that an additional ECG was obtained and the serious adverse event reporting process should be followed, if applicable.

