2. STUDY OVERVIEW

2.1. Study Design

Study 021e is a Phase 3, international, multicenter, open-label, extension study of ataluren in patients with nmCF that have completed participation in the double-blind study PTC124-GD-021-CF (Study 021).

All eligible patients that completed participation in Study 021 will be enrolled into the study. Eligible subjects will receive oral ataluren administered 3 times per day (TID) at respective morning, midday, and evening doses of 10-, 10-, and 20-mg/kg for 96 weeks. The detailed schedule of assessments are displayed in Table 1.

Screening and baseline procedures are structured to avoid a gap in treatment between the double-blind study (PTC124-GD-021-CF) and this extension study. When possible, Screening/Baseline (Visit 1) for this extension study should occur on the same day as the End-of-Study visit for the double-blind study (PTC124-GD-021-CF). During the treatment period, study assessments will be performed at clinic visits at Week 12 and thereafter every 12 weeks until the end of the study.

Planned interim safety analyses will be conducted by an independent data monitoring committee (DMC). The first safety review will occur when ~ 100 patients have completed >=36 weeks of treatment. The second safety review will occur when ~ 100 patients have completed >=72 weeks of treatment.

The study will be terminated prematurely according to company's strategic decision on March 2, 2017. All subject who are on-going by then will be discontinued.

Table 1. Schedule of Events

| Study Period | Screening/B aseline | Treatment Period | | | | | | Post-Treatment | | |
|---|---------------------|------------------|----|----|----|----|----|----------------|-----------------------------|--------------------|
| Study Week (±7 days) | Day 1 | 12 | 24 | 36 | 48 | 60 | 72 | 84 | End of Tx/ Premature D/C 96 | 4 Weeks Post-Tx |
| Visit | 1 | 2 | 3 | 4 | 5 | 6 | 7 | 8 | 9 | 10 |
| Informed consent | X | | | | | | | | | |
| CFQ-R administration | X ^a | X | X | X | X | X | X | X | X | |
| Vital signs | Xa | X | X | X | X | X | X | X | X | X |
| Height | X ^a | X | X | X | X | X | X | X | X | X |
| Weight | X ^a | X | X | X | X | X | X | X | X | X |
| Physical examination | X ^a | | | | X | | | | X | X |
| Hematology | X ^a | X | X | X | X | X | X | X | X | X |
| Biochemistry | X ^a | X | X | X | X | X | X | X | X | X |
| Urinalysis | Xa | X | X | X | X | X | X | X | X | X |
| Renal ultrasound | Xa | | | | X | | | | X | |

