2.3. Study Endpoints

2.3.1. **Primary Endpoint**

• Safety profile characterized by type, frequency, severity, timing, and relationship to ataluren of any adverse events, and laboratory abnormalities

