4.10.2. Clinical Laboratory Evaluations

Hematology laboratory assessments will include white blood cell count with differential, hemoglobin, hematocrit, mean corpuscular volume, mean corpuscular hemoglobin, mean corpuscular hemoglobin concentration, total red cell count with morphology, and platelet count. These parameters will be measured at all study visits.

Biochemistry laboratory assessments will include sodium, potassium, chloride, bicarbonate, blood urea nitrogen, creatinine, magnesium, calcium, phosphorus, uric acid, glucose, total protein, albumin, globulin, albumin:globulin ratio, bilirubin (total, direct and indirect), creatine kinase (CK), lactate dehydrogenase (LDH), alanine aminotransferase (ALT), aspartate aminotransferase (AST), gamma glutamyl transferase (GGT), alkaline phosphatase, total cholesterol, high-density lipoprotein (HDL), low-density lipoprotein (LDL), triglycerides, and cystatin C. These parameters will be measured at all study visits. Ideally, subjects should have fasted for at least 8 hours prior to blood collection.

Urinalysis assessments will include pH, specific gravity, glucose, ketones, blood, protein, creatinine, urobilinogen, bilirubin, nitrite, and leukocyte esterase. These parameters will be measured at all study visits.

Hematology, serum biochemistry, and urinalysis data and their changes from baseline (only for continuous laboratory parameters) will be summarized by visit. Maximal and minimal change from baseline in each parameter will also be summarized.

Shift tables for hematology, serum biochemistry, and urinalysis will also be presented showing change in CTCAE severity grade from baseline to each visit. For parameters for which a CTCAE scale does not exist, shift tables will be presented showing change in results from baseline (normal, low, and high [or abnormal]) to each visit (normal, low, and high [or abnormal]).

Frequency tables will be presented for safety monitoring parameters to show the number and percentages of subjects by severity grade categories defined in Table 2. If a CTCAE grade does not exist, abnormal results will be summarized by protocol-defined thresholds as noted in Table 2. Subjects will be characterized only once for a given assay, based on their worst severity grade observed during the time period of interest.

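### SAP 5.2 labels every early-termination visit as the scheduled visit after the last one attended, with no study-day or on-treatment condition, so by-visit rows, above all Weeks 84 and 96, can hold misdated values

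*SAP*

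**What the plan says.** SAP 5.2 takes the protocol's scheduled visits as analysis visits and says of them: "They are not derived via visit window mapping". An ET visit takes the label of the scheduled visit that follows the last non-missing one. The worked example is at subject level: "For example, if the subject discontinued after Week 12, the early termination visit should be derived as Week 24". The sentence before the ET rule carries a condition that the ET rule lacks: "Final Visit is derived as the last non-missing on-treatment visit during the study for each subject and included into the by-visit summary analyses". The SAP does not define on-treatment.

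SAP 2.1 reports a sponsor decision to terminate the study, with the date 2 March 2017, and adds: "All subject who are on-going by then will be discontinued".

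The primary endpoint (SAP 2.3.1) is "Safety profile characterized by type, frequency, severity, timing, and relationship to ataluren of any adverse events, and laboratory abnormalities". SAP 4.10.2, part of the primary analyses, states: "Hematology, serum biochemistry, and urinalysis data and their changes from baseline (only for continuous laboratory parameters) will be summarized by visit". It also plans shift tables from baseline to each visit. FEV₁ and FVC (SAP 4.11) and vital signs, weight, BMI, ECG and renal ultrasound (SAP 4.12) are likewise presented by visit.

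The protocol gives scheduled visits a ±7-day window (Table 3) but sets no study day for the premature-discontinuation visit. Section 8.2.4 says only that "the procedures that would normally be performed at Week 96 should be performed as a Premature-Discontinuation Visit before the patient leaves the study". Section 8.2.5 foresees an end-of-treatment visit more than 4 weeks after the last dose. On treatment, renal ultrasound (8.2.13) is set for "Week 48 (Visit 5) and Week 96" only, and ECG (8.2.14) for the same two visits.

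**The concern.** A row labelled Week 60 should describe subjects at about 60 weeks of exposure. Under this rule, someone seen one week after Week 48 and then closed out also contributes to Week 60. In an ordinary study with a few dropouts this would be a small blemish. Here the sponsor ended the study for everyone still in it, so the rule governs the last visit of most subjects, and the later the row, the larger its share of relabelled values.

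This is a long-term safety study and timing is part of its primary endpoint. A reader of the late rows would take them as evidence at nearly two years of exposure. For ECG and renal ultrasound, the same rule puts results in rows where the protocol schedules no such test.

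**Working it through.** The plan states no figure to reproduce, so the check is date and schedule arithmetic.

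**Size of the label error for one subject** (visits every 12 weeks, or 84 days):
- Preceding visit on its nominal day: an ET visit 1 to 83 days later is labelled day 84. The maximum gap is 83/7 = 11.9 weeks.
- Preceding visit 7 days early, as Table 3 allows: (83 + 7)/7 = 12.9 weeks.
- Week 12 attended, Week 24 missed, ET between Weeks 24 and 36: the literal label is Week 24, so the value lies 1 to 83 days after its label.

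**Latest reachable visit.** The inputs are the first 021 dose on 15 August 2014 (Protocol 1), 48 weeks of 021 treatment (336 days) and the termination date of 2 March 2017.
- Earliest extension start: 15 Aug 2014 + 336 days = 17 Jul 2015.
- Week 84: + 588 days = 24 Feb 2017, which is 6 days before 2 March 2017.
- Week 96: + 672 days = 19 May 2017, which is 78 days (11.1 weeks) after 2 March 2017.

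On nominal timing, only subjects dosed in 021 within 6 days of the first patient could reach Week 84 by 2 March. That becomes 13 days if the Week 84 visit is 7 days early, and 20 days if the final 021 visit is assumed to have the same allowance. Week 96 stays out of reach in every case. A rollover gap only shortens exposure.

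**Illustration of the other rows.** Assumptions: uniform 021 entry over the estimated 14 months (Protocol 1), no rollover gap, no earlier dropout, ET on 2 March 2017.
- The last entrant starts the extension on 15 Oct 2015 + 336 days = 15 Sep 2016, giving 168 days = 24.0 weeks. The first has 594 days = 84.9 weeks. Exposure E is uniform on 24.0 to 84.9, a range of 60.9 weeks.
- ET share of row k = P(k−12 ≤ E < k) / P(E ≥ k−12).

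| Row | Calculation | ET share |
|---|---|---|
| Week 36 | 12/60.9 | 20% |
| Week 48 | 12/48.9 | 25% |
| Week 60 | 12/36.9 | 33% |
| Week 72 | 12/24.9 | 48% |
| Week 84 | 12/12.9 | 93% |
| Week 96 | 0.9/0.9 | 100% |

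ET values fall on average 6.1 weeks before their label, and 92% lie outside ±7 days.

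**Sensitivity.**
- Dropout of 10% or 20% by Week 48: the shares become 22–24, 27–29, 34–36, 50–51, 93–94 and 100%.
- Accrual stretched to 14 × 279/208 = 18.8 months: Weeks 12 and 24 are added (11% and 16%), and later rows do not change.
- Closing visits due within 2, 4, 6 or 8 weeks held on schedule: the proportion outside ±7 days falls from 92% to 84, 67, 51 or 34%. The misdated share of the Week 84 row falls from 86% to 78, 62, 47 or 31%.

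**ECG and ultrasound, subject-level reading, same base case.** Labels at Weeks 36, 60, 72 and 84 take 4 × 19.7% = 79% of ET results, and none of these visits has a scheduled test.

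**Effect on mean FEV₁.** At the Study 009 ataluren rate (−2.5% relative change in 48 weeks, Protocol 15.2): 2.5/48 × 6.1 = about 0.3%.

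**The case against.** The strongest reply is that little harm is shown. Every analysis is descriptive (SAP 4.2), and the FEV₁ t-test and completer analyses have been dropped (SAP 6). The main safety outputs do not use the label: adverse event tables, exposure-adjusted rates, worst-grade laboratory tables, maximal and minimal changes, and Final Visit. The mean FEV₁ shift is small. The SAP also offers laboratory and vital-sign descriptions by duration of exposure, by-subject listings and a count of subjects at each visit. All of this stands and limits the seriousness. It does not repair the rows: the exposure summaries are only as necessary, and a printed n shows that a row is small, not that its contents are misdated.

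The second reply is that the row shares are model output. That also stands. The recruitment period is an estimate, rollover gaps are possible (Protocol 7.1.2), and 2 March 2017 may date the decision and not the visits, since the sponsor sets the period for contacting patients (Protocol 13.9). The finding for Weeks 84 and 96 needs no accrual curve, but it does depend on how long closing visits continued.

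Third, one could simply flag ET values or add a table without them. That would disclose the problem at less cost but leave misdated values in the main tables.

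Two stronger readings are tempting. A reader might infer that a scan after Week 48 would be labelled Week 96, up to 48 weeks early, by applying the rule test by test. The SAP derives a visit for a subject, and its example uses Weeks 12 and 24, where neither test is scheduled, so the text does not support that reading. A reader might also infer that the rows are heavily contaminated with off-drug values. Protocol 8.2.5 shows only that such visits can occur; how often is unknown.

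**Conclusion.** The point holds and should be fixed before database lock, though it is not critical. The rule is explicit, nothing else in either document limits it, and it can misdate a by-visit value by about 12 weeks (12.9 with the visit window), usually too early but too late after a missed visit.

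The firmest consequence is in the late rows. Unless closing visits ran well past 2 March 2017 (by 11 weeks or more for Week 96), Week 96 is wholly relabelled ET data, and Week 84 is mostly so unless many closing visits were held on schedule after that date. This rests on the first-dose date, 48 weeks of prior treatment and nominal timing. Shares for Weeks 36 to 72 are illustrations under uniform accrual and should not be quoted as facts about the trial.

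The documents do not support inferring that the overall safety conclusions are compromised. The effect is confined to descriptive by-visit summaries and shift tables.

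**What to change.** Replace the last two sentences of SAP 5.2 with:

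> An on-treatment early-termination assessment enters a scheduled-visit row only if its actual study day is within ±7 days of a visit at which that assessment is scheduled and that visit has no value. Otherwise it is reported in the Final Visit row, which is included in all by-visit summaries and shift tables, including ECG and renal ultrasound. Early-termination assessments that are not on-treatment are shown in a separate off-treatment early-termination row.

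State one numeric on-treatment limit, in days after the last dose, and use it for both Final Visit and ET data. Borrowing the 4-week adverse event window would count values taken up to 4 weeks off drug as on-treatment. The separate off-treatment row is needed because renal ultrasound has no scheduled post-treatment visit.

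The cost is SAP wording and one derivation. On-treatment values stay in Final Visit and off-treatment values in their own row. The downside is that late scheduled rows become small or empty. In the base case, per 200 subjects, the rows change as follows: Week 36 from 200 to 164, Week 48 from 161 to 124, Week 60 from 121 to 85, Week 72 from 82 to 46, Week 84 from 42 to 6, and Week 96 from 3 to 0. Each ET value that remains in a scheduled row is then within ±7 days of its label.
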